ICU-free days at Day 28 and at hospital discharge (days) [study day based on Date]	
ICU-free days at Day 28
 
If patient is alive at Day 28 (last available day \geq 26) and ICU-free days is not missing at Day 28: ICU-free days = 28 – ICU stay up to Day 28.[^]
 
Else, If patient is discharged before Day 28 (date of discharge is not missing and date of discharge $<$ Day 28) and the patient died after hospital discharge and before day 28 (hospital discharge $<$ date of death $<$ Day 28) then ICU-free days at day 28= ICU-free days at discharge
 
If patient dies within Day 28 : ICU-free days = 0
 
If subject is alive and followed for $<$ 26 days (last available date $<$ 26) the endpoint is set as missing.
 
Otherwise, the endpoint will be set as missing.
 
[^]in case of negative values, it is assumed that ICU-free days = 0.
 
Day 28= Day 1 date + 27
 
ICU-free days at Hospital Discharge
 
If patient is alive at hospital discharge date* (last available date $>$ hospital discharge date*): ICU-free days = [hospital discharge date* – First IMP Intake date + 1] – ICU stay up to hospital discharge date*. [^]
 
If patient is never discharged (date of discharge is missing) and the patient died after day 28 (date of death $>$ Day 28), then ICU-free days at discharge=ICU-free days at day 28
 
Else (If patient dies within hospital discharge date*) or (if date of death is not missing and it is prior to Day 28 (date of death $<$ Day 28) and discharge date is missing (i.e., subjects died during hospitalization)): ICU-free days = 0
 
Otherwise, the endpoint is set as missing.
 
[^]in case of negative values, it is assumed that ICU-free days = 0.
 
*date of discharge is collected in End of Study form; in the case it is missing it is taken from Visit date in "Hospital Discharge".

Standard/Forms/Template				
Title		Statistical Analysis Plan Template		
Code		Version	Effective Date	Page
PPD		01	29 Aug 2022	65 of 78

Parameter	Calculation

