Hospital stay up to Day 28 (days) [study day based on Date]	
Hospital stay up to Day 28 :
 
Date of discharge* – First IMP Intake date + 1.
 
If Date of discharge* is after Day 28 date, then Day 28 date will be used instead.
 
If Date of discharge* is missing and date of death\geq Day 28 date then date of Discharge = Day 28 date.
 
If Date of discharge* is missing and last available day \geq 26 then date of Discharge = Day 28 date.
 
Otherwise the endpoint is set as missing.
 
Day 28 date: Day 1 date + 27
 
*date of discharge is collected in End of Study form; in the case it is missing it is taken from Visit date in "Hospital Discharge".

Hospital-free days by Day 28 [study day based on Date]	
Hospital-free days by Day 28
 
If patient is alive at Day 28 (last available day \geq 26): Hospital-free days = 28 – Hospital stay up to Day 28
 
If patient dies within Day 28: Hospital-free days = 0
 
Otherwise, If subject is alive and followed for $<$ 26 days (last available day $<$ 26) the endpoint is set as missing.
 
Day 28= Day 1 date + 27

Standard/Forms/Template				
Title		Statistical Analysis Plan Template		
Code		Version	Effective Date	Page
PPD		01	29 Aug 2022	66 of 78

Parameter	Calculation
Patients discharged (alive) by Day 28 [study day based on Date]	
A patient is considered discharged alive by Day 28:
 
 - if patient is discharged* before Day 28 (included) (regardless the vital status after discharge). 
Otherwise, a patient is considered not alive and discharged by Day 28:
 
 - if patient dies and date of discharge* is missing, OR - if patient is not discharged* before Day 28 (included) (day of discharge >28) OR - if date of discharge is missing, but subject is in study long enough (last available day ≥ 26) OR - Discharge date=Death date (assumptions: patient died in the hospital) 
Otherwise, if the date of discharge is missing and subject is alive and followed for <26 days (last available date<26) the endpoint is set as missing.
 
Day 28: Day 1 + 27
 
*date of discharge is collected in EOS; in the case it is missing it is taken from Visit date in "Hospital Discharge".

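### SAP Table 3, discharged alive by Day 28: the line that excludes in-hospital deaths sits behind the branch that has already accepted them

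*SAP*

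**What the plan says.** SAP section 11.1.1, Table 3, defines the secondary endpoint of patients discharged alive by Day 28 as an ordered rule with Day 28 = Day 1 + 27.

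1. **First branch, scored discharged alive:** any patient discharged "before Day 28 (included) (regardless the vital status after discharge").
2. **Second branch, scored not discharged alive.** It opens with "Otherwise, a patient is considered not alive and discharged by Day 28" and lists four alternatives. The ones that matter here are:
   - "if patient dies and date of discharge* is missing, OR"
   - "if patient is not discharged* before Day 28 (included) (day of discharge >28) OR"
   - last in the list, "Discharge date=Death date (assumptions: patient died in the hospital").
3. **Third branch:** set to missing, for a patient alive with no discharge date and too little follow-up.

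A footnote gives the source: "date of discharge is collected in EOS; in the case it is missing it is taken from Visit date in" the Hospital Discharge form. SAP 7.2.1.14 compares the resulting proportions with Fisher's exact test. SAP 4.2.4 places secondary efficacy results on the FAS.

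The row for ICU-free days at hospital discharge, in the same table, begins with a survival check: "If patient is alive at hospital discharge date* (last available date" later than the discharge date). It gives 0 to a patient who dies on or before that date.

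**The concern.** The equal-dates line shows that the authors expected some in-hospital deaths to carry a discharge date and meant to count them as not discharged alive. The line is placed where it cannot do that. The first branch looks only at the discharge date and sets aside vital status after discharge; it never asks whether the patient was alive at discharge. A patient who meets both the first branch and the equal-dates line has been classified before the second is read.

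The result would be deaths counted as successes in one secondary endpoint while the ICU-free-days row treats the same patients as in-hospital deaths. Two competent programmers could also code the row differently, one following the order and the other the apparent intent.

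**Working it through.** The plan states no figure for this endpoint, so there is none to reproduce. The check is of the decision logic.

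**Method.** The rule was coded in the written order and run over every combination of discharge day (missing, or 1 to 60) and death day (none, or 1 to 60), with survivors taken as followed to Day 60. That is 61 × 61 = 3,721 date pairs. These are possible date patterns, not patients. Two alternatives were then run: the equal-dates line moved to the front, and a test of discharge on or after death at the front.

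**Written order.**
- The equal-dates line decided 0 of the 3,721 pairs.
- Of the 60 equal-date pairs, 28 (Days 1 to 28) were scored discharged alive by the first branch. The other 32 (Days 29 to 60) were scored not discharged alive by the earlier item for discharge after Day 28, so the equal-dates line is redundant there.
- Pairs with discharge after death number 60 × 59 / 2 = 1,770. Of these, 28 × 27 / 2 = 378 have discharge by Day 28, and all 378 were scored discharged alive. The remaining 1,392 were not.

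**Example pairs** (yes = scored discharged alive):

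| Discharge day | Death day | As written | Equal-dates line first | Discharge ≥ death tested first |
|---|---|---|---|---|
| 10 | 10 | yes | no | no |
| 28 | 28 | yes | no | no |
| 29 | 29 | no | no | no |
| 12 | 10 | yes | yes | no |
| missing | 10 | no | no | no |
| 10 | 12 | yes | yes | yes |

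Moving the existing line to the front repairs the equal-date case but leaves all 378 pairs with discharge after death, because that line tests equality only. Testing discharge on or after death repairs both. A true death after discharge (discharge Day 10, death Day 12) stays discharged alive throughout, as the SAP intends.

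**Against the ICU-free-days row.** Take death and discharge both on Day 10. By the Table 3 definition, the last available date of a patient who dies is the date of death, here Day 10. It is not later than the discharge date, so the survival check fails and ICU-free days at discharge are 0. In the discharged-alive row, Day 10 ≤ Day 28, so the first branch returns discharged alive.

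**Size per patient.** SAP 3.1 plans about 66 patients at 1:1, so about 66 / 2 = 33 per arm. One misclassified patient moves that arm's proportion by 1 / 33 = 3.0 percentage points.

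**The case against.** The best defence is that the row is prose, not code. Its title carries the word alive, the first branch disregards vital status only after discharge, and the equal-dates line says outright that such a patient died in hospital. On that reading the specific line limits the general one, and the flaw is one of drafting. This shows what the sponsor meant, and it should settle how the rule is corrected. It does not repair the order: *Otherwise* gives the first branch priority, and the intended reading has to be supplied by the programmer.

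Other parts of the defence stand.

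- The SAP often treats an in-hospital death as having no discharge date (the ICU-free-days and secondary-infections rows of Table 3). The discharged-alive row scores that pattern correctly.
- A discharge dated after death is an impossible sequence. Protocol 11.2 provides edit checks for logic, and SAP 4.12 a blinded data review before lock. Nothing in the documents suggests that sites will record such dates.
- Deaths are reported separately at Days 28 and 60, and hospital-free days give 0 to any death by Day 28, so mortality is not hidden.

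A reader might infer more than the documents support:

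- **A large bias.** Protocol 2.6.2.3 quotes ARDS mortality of 27% to 45%, which for 66 patients is about 18 to 30 deaths. That figure is not stated as in-hospital mortality by Day 28, and no document gives the share of deaths that will carry a discharge date. Any percentage built from it rests on an invented share.
- **An advantage to the arm with more deaths.** This would need the share of deaths with a discharge date to be similar in the two arms, which is not known.
- **Every in-hospital death affected.** The tracheostomy and LTAC rows set a missing discharge date to the death date. If that were carried into a shared variable the problem would spread, but it is written as a note within those rows, and the discharged-alive row tests for a missing discharge date, so it evidently uses the unfilled one.

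**Conclusion.** The point holds as a fault in the written order. For a discharge date by Day 28 equal to the death date, the rule returns discharged alive, contrary to the intent stated in the same row and to the ICU-free-days row. For later dates the equal-dates line changes nothing. A discharge date after death and by Day 28 escapes every line, but that is a data-error case rather than one the plan anticipates.

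The number of patients affected cannot be determined from the documents and may be zero. It depends on whether sites enter a discharge date for patients who die in hospital. Each such patient by Day 28 adds about 3 percentage points to an arm's proportion, assuming about 33 per arm as planned. The endpoint is secondary and descriptive, and the primary endpoints are untouched. This is a minor correction worth making because it costs so little.

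**What to change.** Test death first in the Table 3 row:

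1. If the date of death is on or before the discharge date, score not discharged alive.
2. Score discharged alive only if the discharge date is on or before Day 1 + 27 and the date of death is either missing or later than the discharge date.
3. Then apply the remaining branches as they stand. The equal-dates line can be deleted, since step 1 covers it.

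Query any record with a discharge date after the death date before database lock. If the endpoint has already been programmed, check which order the program follows, list patients whose death date is on or before their discharge date, and explain any departure from the SAP in the CSR, as SAP section 1 requires.

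The cost is one reordered derivation, one added condition and one data check. No new data are needed.

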4.10 Handling of missing and incomplete data

All reasonable efforts will be made to reduce the rate of missing data. Investigators will be trained about the importance of patient retention and full data capture. Also, any reasonable attempts should be made by the investigators to emphasize continued subject's participation for the full duration of the trial.

Patients who discontinue the treatment will not be withdrawn from the study by default, but will be asked to complete safety and efficacy observations as per the protocol, unless otherwise they withdraw their consent. Patients who discontinue study treatment and decide to remain in the study by following the schedule of assessments and continuing to adhere to protocol requirements are defined as "retrieved dropout" patients (section 11.1.1 provides details on the definition).

For the main analyses of the primary endpoints, missing data will be managed as follows:

- Missing data due to death, preventing the collection of the endpoint, will be imputed with an unfavourable value (see section 4.4.1).
- Missing data in extubated patient, preventing the collection of the endpoint (for Change in OI at Day 7 only), will be imputed with a favourable value (see section 4.4.1).
- Missing data due to treatment discontinuation or any other reason (whichever the reason) will be handled by means of Multiple Imputation (MI) approach as detailed in Section 7.1.1.

Sensitivity analysis of the primary endpoints can be based on different missingness assumptions (section 7.1.2.1)

In the descriptive summaries, the number of subjects with missing data will be presented under the "Missing" category. Missing values will be included in the denominator count when computing percentages. When continuous data will be summarized, only the non-missing values will be evaluated for computing summary statistics. Any exception will be declared.

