7.2 Analysis of secondary efficacy endpoints

7.2.1 Analysis details

Independently of results on primary, all secondary endpoints (Section 0) will be analyzed and compared by treatment by means of descriptive statistics and by appropriate parametric tests depending on the nature of the variable and its distribution. No multiplicity correction is required. Statistical tests for continuous variables will be performed only for the change from baseline.

The assumption of normality requested by parametric statistical tests, will be checked as described in section 4.1, and in case such assumptions are not met, also non-parametric counterpart tests will be performed. Change from baseline value (for continuous variables) and shift tables versus baseline (for categorical variables) may also be summarized for all post-baseline visits, as described in the following sections. Alpha level to be used for secondary endpoints is 0.05 two-sided.

7.2.1.1 Change in OI from baseline to Day 4

Value and change in OI from baseline to Day 4 will be analyzed by means of descriptive statistics as a continuous variable. Comparison between treatments will be performed by means of two-sample t-test and, if assumptions of normality is not confirmed, two-sample Mann-Whitney U test.

Change from baseline to Day 4 is derived similarly to change from baseline to day 7: details on derivation are provided in section 11.1.1.

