7.2.1.5 Incidence of ECMO

Rules for derivation of Incidence of ECMO are reported in section 11.1.

The number and proportion of patients requiring ECMO will be reported at Day 14 and compared by means of Fisher's exact test or Chi-squared test, depending on data distribution.

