7.2.1.6 Use of vasoactive medications

Vasoactive medication use will be defined as described in Section 11.1.

The proportion of patients with at least one vasoactive medication by Day 14 (as defined in section 11.1.1) will be compared by Fisher's exact test or Chi-squared test, depending on data distribution.

7.2.1.7 CXR assessment of pulmonary edema by “radiographic assessment of lung edema” (RALE) score

Value and change from baseline in RALE score will be analyzed at Day 2, Day 3, Day 7, Day 14 (if still intubated) timepoints by means of descriptive statistics as a continuous variable. Comparison between treatments will be performed by means of two-sample t-test and, if assumptions of normality is not confirmed, two-sample Mann-Whitney U test.

7.2.1.8 Percentage of patients achieving pressure support ventilation equal to 5 cmH₂O with PEEP equal to 5 cmH₂O for 2 hours (measure of weaning) by day 28 and at hospital discharge

The proportion of patients achieving pressure support ventilation equal to 5 cmH₂O with PEEP equal to 5 cmH₂O for 2 hours (measure of weaning) by Day 28 and at hospital discharge will be compared by Fisher's exact test or Chi-square's test, depending on data distribution.

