Last available date	
Most recent visit date/assessment date/procedures date (max: end of study date) defined as follows.
 
last available date = end of study (EOS) date*
 
If reason for discontinuation = “Lost to follow-up”, last available date=most recent visit date§ or assessment date^ or procedures date
 
*For patient who dies: end of study date = date of death
 
§ at Day 60 visits to be considered only if patient Vital Status = “Alive” in the form “Follow-Up”
 
^assessment including information from all summary pages (AEs, CM...)

Last available day	
Last available date – Day 1 date + 1
 
Note: Day 1 date for derivation of the Last available day is based on calendar day (i.e., date of first IMP)

Time from Date of diagnosis of moderate to severe ARDS to randomization	
Randomization date – Date of diagnosis of moderate to severe ARDS + 1.
 
CRF field: “Date of diagnosis of moderate to severe ARDS as defined in inclusion criterion 3” in “ARDS-SPECIFIC INFORMATION” CRF form

Extent of exposure (hours)	
Exposure calculated as total number of hours under treatment: (Date:time of last administration of IMP – Date:time of first administration of IMP)
 
Date/time first and last administration defined in SAP 3.1.1
 
Date/time first administration of IMP missing:
 
If Date first administration of IMP is not missing and time first administration of IMP is missing then:
 
If Date first administration of IMP = “Date of Randomization” and Time randomization is not missing then time first administration of IMP= time of randomization;
 
Otherwise set time first administration IMP = “00:00”
 
Date/time last administration missing:
 
If Time last administration of IMP is missing then set time last administration IMP = “23:59”

Total number of tablets scheduled during the treatment period	
[ROUND(Extent of exposure (hours)/8) + 1]*2
 
The result has to be taken rounded to the closest integer.

Extent of exposure (days)	Date of last administration of IMP – Date of first administration of IMP + 1.

Standard/Forms/Template				
Title		Statistical Analysis Plan Template		
Code		Version	Effective Date	Page
PPD		01	29 Aug 2022	59 of 78

Parameter	Calculation

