Incidence of ECMO by day 14 [study day based on Date]	
Transition to ECMO (Y/N) is collected in "Ventilation - Specific Information" CRF Daily assessments through extubation.
 
Incidence of ECMO at Day 14 :
 
event = "Y" if Transition to ECMO = "Y" and date of daily collection (VSIDAT) is performed between date of 1st IMP intake and Day 14 included.
 
otherwise
 
event = "N" if last available day ≥ 12 (allowed time window of 2 day for Day 14 visit)
 
otherwise event is missing if last available day < 12
 
Day 14= Day1 (date 1st IMP intake) + 13

Standard/Forms/Template				
Title		Statistical Analysis Plan Template		
Code		Version	Effective Date	Page
PPD		01	29 Aug 2022	67 of 78

Parameter	Calculation
Use of Vasoactive Medication by day 14 [study day based on Date/time]	
Use of Vasoactive Medications is collected in "Ventilation - Specific Information" CRF Daily assessments through extubation.
 
Use of Vasoactive Medications by Day 14 :
 
event = "Y" if Vasoactive Medications = "Y" and date/time of daily collection is performed between Date/time of 1st IMP intake and Day 14 (date/time).
 
otherwise
 
event = "N" if last available day>=12 (allowed time window of 2 day for Day 14 visit)
 
otherwise event is missing if last available day<12
 
Day 14= Day1 (date/time 1st IMP intake) + 13

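### ECMO and vasoactive use by Day 14: an event-free death on Days 1–11 is coded missing while a death after the event counts as Y, so the test comparison loses only non-events

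*SAP*

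**What the plan says.** In the ECMO row of SAP 11.1.1 (Table 3), a patient gets one of three values.

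- **Y:** "event = 'Y' if Transition to ECMO = 'Y' and date of daily collection (VSIDAT) is performed" between first IMP intake and Day 14. There is no condition on survival or length of follow-up.
- **N:** no such record, and a last available day of 12 or later. The 12 is explained as "allowed time window of 2 day for Day 14 visit".
- **Missing:** "otherwise event is missing if last available day < 12".

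The row for vasoactive medication has the same three branches, using date and time. The entry for last available date in the same table adds: "For patient who dies: end of study date = date of death".

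On analysis, SAP 7.2.1.5 states: "The number and proportion of patients requiring ECMO will be reported at Day 14 and compared by means of" Fisher's exact or chi-squared test. SAP 7.2.1.6 states: "The proportion of patients with at least one vasoactive medication by Day 14 (as defined in section 11.1.1) will be compared by" the same tests. For descriptive summaries, SAP 4.10 states: "Missing values will be included in the denominator count when computing percentages". SAP 7.2.1 adds: "Alpha level to be used for secondary endpoints is 0.05 two-sided". SAP 3.3 specifies no hypotheses and treats p-values as descriptive.

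**The concern.** A patient who dies on Day 5 without ECMO has a known outcome: no ECMO before death, and none possible afterwards. Both items are collected daily while the patient is intubated. The rule nevertheless treats this patient as unknown, while a patient who dies on Day 5 after starting ECMO is counted. Missingness therefore depends on the outcome, and only non-events leave the comparison. If event-free early deaths are more frequent in one arm, two arms with equal event rates can look different in the test.

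**Working it through.** The documents give no expected rate for either event, no early-death rate and no power for these endpoints, so there is no planned figure to reproduce. All rates below are assumptions.

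**1. Tracing the rule.**

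| Patient | Last available day | Event recorded | Code |
|---|---|---|---|
| Dies Day 5 | 5 | yes | Y |
| Dies Day 5 | 5 | no | missing |
| Dies Day 13 | 13 | no | N |
| Alive, lost on Day 5 | 5 | yes | Y |
| Alive, lost on Day 5 | 5 | no | missing |

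Only deaths on Days 1–11 are affected. No other SAP text gives the second patient a value.

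**2. Comparison with neighbouring rows of SAP 11.1.1.** Ventilator-free and hospital-free days score death within 28 days as 0 and reserve missing for living patients followed for less than 26 days. ICU-free days do the same, with a separate rule for death after discharge. Tracheostomy and LTAC transfer by hospital discharge use the death date as the discharge date when the latter is absent, so an event-free death is N.

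**3. Size.** Let n be the patients in an arm, Y those with the event, and m those event-free with last available day below 12. With missing patients dropped, the tested proportion is Y/(n−m). Relative to Y/n it is raised by n/(n−m). About 66 patients at 1:1 (SAP 3.1) gives n = 33:

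- m = 2: 33/31 = 1.065
- m = 4: 33/29 = 1.138
- m = 6: 33/27 = 1.222
- m = 8: 33/25 = 1.320

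**4. Two examples with equal true counts.**

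- ECMO, 3 of 33 in each arm (9.1%), m = 3 and 8: tested 3/30 = 10.0% against 3/25 = 12.0%; Fisher p = 1.0.
- Vasoactive use, 23 of 33 in each arm (69.7%), m = 1 and 4: tested 23/32 = 71.9% against 23/29 = 79.3%; Fisher p = 0.56.

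**5. Does the rule match any sensible target?** Take constant event hazard λ and death hazard μ over one window of unit length (ignoring the Day 12 to 14 allowance). Cumulative incidence is A = λ/(λ+μ) × (1 − e^−(λ+μ)). Event-free survival is S = e^−(λ+μ). The rule estimates A/(A+S). Treating death as censoring gives 1 − e^−λ (1 − KM).

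| Setting | Early mortality | Rule | Cumulative incidence | 1 − KM |
|---|---|---|---|---|
| ECMO-like, λ = 0.105 | 9.5% | 10.4% | 9.5% | 10.0% |
| | 18.1% | 10.9% | 9.0% | 10.0% |
| | 29.5% | 11.7% | 8.4% | 10.0% |
| Vasoactive-like, λ = 1.2 | 9.5% | 71.1% | 67.2% | 69.9% |
| | 18.1% | 72.4% | 64.6% | 69.9% |
| | 29.5% | 74.2% | 61.0% | 69.9% |

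The rule lies above both references, and the gap widens with mortality.

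**6. Effect on the test.** Simulation of 20,000 trials, 33 per arm, equal true Y rates, Fisher at p < 0.05:

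| True Y rate | m, arm 1 / arm 2 | Rejections, missing dropped | Rejections, coded N |
|---|---|---|---|
| 10% | 10% / 30% | 3.7% | 1.1% |
| 30% | 10% / 30% | 8.6% | 2.6% |
| 50% | 5% / 25% | 14.2% | 3.3% |

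**The case against.** Four points can be made for the plan.

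**The reported incidence is not inflated.** A reader might infer that the published percentages will be too high. SAP 4.10 rules that out, because missing patients stay in the denominator: in the ECMO example the table would show 9.1% in both arms. Nor does the SAP say that the tests drop missing patients. That is the ordinary reading, but it is an inference. What stands is narrower: the test is affected on that reading, and the table would then use a different denominator.

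**More early deaths need not mean more distortion.** The driver is event-free early deaths. Suppose one arm has 8 early deaths, all on vasoactives (m = 0), and the other has 3, of which 2 are event-free. With 23 events in each, the tested proportions are 23/33 = 69.7% and 23/31 = 74.2%, so the arm with fewer deaths is inflated. Size depends on the same link. With true use of 60% and 20% early deaths, independence of event and death gives 0.60/(1 − 0.2 × 0.4) = 65%. If 90% of those early deaths had the event, the result is 0.60/(1 − 0.2 × 0.1) = 61.2%. For vasoactive use the second case is plausible.

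**Coding N is itself an estimand choice.** Death then competes with the event and can make the arm with more deaths look better. In step 5, cumulative incidence falls as mortality rises, and for vasoactive use it lies further from 1 − KM than the rule does. This is a real cost, but it does not rescue the rule, which estimates neither quantity.

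**Little depends on it.** These are secondary, descriptive endpoints; mortality by Day 28 and Day 60 is analysed separately; and the higher rejection rates need a 20-point difference in event-free early loss, which nothing in the documents supports. This stands and limits the weight of the point.

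**Conclusion.** The asymmetric coding is certain from the SAP text. On the usual reading that missing patients are dropped, the direction is certain too: the tested proportion can only rise, by n/(n−m). Its size is not known. At 33 per arm the factor is 1.14 for m = 4 and 1.32 for m = 8, but the documents give no basis for m; protocol 2.6.2.3 cites overall ARDS mortality of 27% to 45% without the share before Day 12. Unequal distortion requires different numbers of event-free early losses between arms. If nearly all early deaths had the event, the effect is small. The documents do not support the stronger conclusions that displayed incidence is inflated or that the arm with more early deaths is always the more affected. The impact is modest and no primary result depends on it, but the rule serves no clear target and is cheap to correct.

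**What to change.** In both rows of SAP 11.1.1:

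- Code an event-free death before Day 12 as N, meaning that the event did not occur before death by Day 14.
- Set missing only if the patient is alive and the last available day is below 12, in line with the rows for ventilator-free, ICU-free and hospital-free days.
- State one denominator and use it for both the table and the test. SAP 4.10 allows exceptions to its percentage rule if declared.

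If all of m are deaths, the examples in step 4 return to 3/33 = 9.1% and 23/33 = 69.7% in both arms. The few living patients lost early would still be Y or missing and should be counted in a footnote.

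The cost is one clause in each of two rows and one sentence on the denominator; no new data are needed. The downside is that death then acts as a competing event that can lower apparent use, so the results should be read beside mortality. A supportive composite of event or death by Day 14 would be a useful option.
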